4.0 STUDY OBJECTIVES

4.1 Primary Objective

To evaluate the degree to which a brief, combined group-plus-individually delivered 12-step facilitative intervention (STAGE-12), integrated into treatment as usual, reduces the percent of days of stimulant drug use for participants with stimulant abuse or dependence disorders compared to treatment as usual (TAU).

4.2 Secondary Objectives

- To evaluate the degree to which STAGE-12, integrated into treatment as usual, reduces the
 percent of days of use of non-stimulant drugs for participants with stimulant abuse or
 dependence disorders compared to TAU.
- To evaluate the degree to which STAGE-12, integrated into treatment as usual, increases involvement in 12-step activities, meeting attendance, and acceptance of 12-step beliefs and values, compared to TAU.
- To examine client attitudes and beliefs as mediators of 12-step meeting attendance and involvement.
- To examine 12-step meeting attendance and involvement as mediators of substance use outcomes
- To examine the relative differences in 12-step meeting attendance and involvement and substance use outcomes of different client subtypes (e.g., ethnic/racial groups, gender, drug of choice, psychiatric severity, readiness to change).

5.0 STUDY DESIGN AND STUDY PROCEDURES

5.1 Overview of Study Design

This is a randomized, two-group, intent-to-treat study evaluating the effectiveness of a combined group-plus-individual intervention, Stimulant Abuser Groups to Engage in 12-Step (STAGE-12), on stimulant use outcomes. The STAGE-12 intervention is integrated into treatment as usual by replacing 8 (5 group and 3 individual) treatment sessions, in the site-specific treatment as usual, over a maximum of 8 weeks. The STAGE-12 intervention is meant to facilitate involvement in 12-step activities and attendance at 12-step self-help meetings. The comparison group will be treatment as usual without STAGE-12 (TAU). TAU will consist of the standard therapy offered by the site(s) over the 8-week period. The study consists of three phases: the screening/baseline phase, the treatment phase, and the follow-up phase. A diagram of the study schema is presented above in Figure 1 in Section 2.

5.1.1 Screening/Baseline Phase

Study participants will be recruited from individuals with stimulant abuse or dependence disorders that are seeking admission or are being enrolled into outpatient substance abuse treatment, including regular outpatient, intensive outpatient, day hospital, or partial hospital programs, at participating CTPs.

The study research staff will explain the protocol to the prospective participants and obtain informed consent and HIPAA authorization (if applicable). Those who complete the consent process will proceed to the screening/baseline phase of the study. The inclusion and exclusion criteria for the participants are given in section 5.3.3.1 below. Further, information collected during this phase will also be used in the randomization process (section 5.1.2.2) to assign those individuals who meet study inclusion criteria to one of the two treatment conditions. The randomization procedure is meant to balance the treatment conditions within CTPs.

5.1.2 Randomization

5.1.2.1 Counselor Randomization

All counselors within a CTP who are interested in potentially participating in the protocol must provide informed consent and sign consent forms. Those who complete the battery of clinician measures, meet the basic eligibility criteria, and volunteer to participate in the trial will serve as a pool within each CTP from which a minimum of two counselors will be chosen randomly to provide the STAGE-12 intervention. A computerized randomization application managed by the Data and Statistics Coordinating Center (DSC) will be used to select the STAGE-12 counselors from this pool. Given that a condition for inclusion in the pool of potential study counselors is completion of the counselor assessments, it will be possible to compare those randomly chosen to serve as STAGE-12 counselors with those who were not chosen on a number of demographic, experience, counseling skills, and therapeutic orientation variables. Those not chosen to serve as STAGE-12 counselors will continue with standard clinic care and will not provide additional data for the study.

5.1.2.2 Participant Randomization

Participants will be randomized after completing the initial eligibility screen, baseline data collection, and a check to be sure that they are still attending outpatient treatment in the participating CTP. Participants will be randomized to one of the two treatment conditions (TAU or STAGE-12) after

completion of baseline assessments. The randomization process will be conducted in a centralized process through the Data and Statistics Center (DSC). Randomization will be stratified by site and by participants court-mandated to treatment vs. participants not court mandated to treatment.

5.1.3 Treatment Phase

The second phase of the study (the "treatment phase") begins after a participant has successfully completed the baseline assessments and has been randomized to one of the two treatment conditions. Counselors from the participating CTP will deliver the treatments: TAU at the participating CTP or STAGE-12. All research participants will receive treatment as usual at the participating CTP, which provides at least 2 sessions per week during the intervention phase. STAGE-12 will consist of 3 individual sessions lasting approximately 45-75 minutes each plus 5 group sessions, each lasting approximately 90 minutes. The STAGE-12 sessions will replace 8 TAU sessions for those participants randomized to this treatment arm. The comparison condition will be TAU without the integrated STAGE-12 sessions.

The group component of the STAGE-12 intervention will be guided by procedures developed by Brown and colleagues (Brown, Seraganian et al., 2002; Brown, Seraganian et al. 2002) for the delivery of TSF in a group format. The three individual sessions will include the introductory and termination sessions from the TSF manual and will integrate the procedures developed by Timko (Timko, DeBenedetti et al. 2006) for the delivery of the intensive referral intervention. A number of within-treatment process variables will be assessed during this active intervention phase, including an assessment of counselors' adherence to the intervention guidelines.

For the purposes of assessments, the "end of treatment" will be standardized across conditions by setting it relative to the completion of the active treatment phase, at 8 weeks post-randomization.

5.1.4 Follow-Up Phase

The third phase of the study involves follow-up assessments of participants. Participants will be followed during visit windows at 3-months and 6-months post-randomization.

5.1.5 Discontinuation, Termination and Participant Replacement

5.1.5.1 Therapy Discontinuation

Participants must be discontinued from the treatment portion of the study if they experience significant physical or psychiatric conditions such that, in the judgment of the site Principal Investigator (PI) and/or the Lead Investigator, continuation in the clinical arm of the trial is contraindicated. Other reasons for considering possible discontinuation include non-compliance with research protocol requirements or a serious adverse event (SAE) that places the participant at risk should he or she continue in the study therapy. Participants who experience deterioration of their clinical status that temporarily results in more intensive level of care (e.g., detoxification, inpatient treatment) may return to the treatment protocol (within 8 weeks of randomization) following stabilization. Individuals who are discontinued from the treatment will be encouraged to complete all follow-up assessments.

5.1.5.2 Study Termination Criteria

Participants are free to withdraw their consent from further participation in the study at any time without cause and without penalty from the CTP where they are receiving their drug abuse treatment. Participants may be involuntarily terminated from all study activities if the site staff, with possible consultation with the Lead Investigator, deems that further participation will be harmful to the participant or for reasons consistent with CTP discharge policies on violence, drug sale, etc.

Once randomized, the clinical deterioration, substance use, and the potential need for more intensive care will be captured in assessments and in the Treatment Services Review (TSR). Reasons for refusal or withdrawal will be documented.

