5.1.5.3 Replacement of Participants

In this intent-to-treat design, all randomized participants will be followed for all possible assessment points. Participants who are randomized to the STAGE-12 intervention but do not attend the initial individual session will not be replaced. Consistent with the intent-to-treat design, attempts will be made to follow these non-attenders in the follow-up assessments and they will be included in the intent-to-treat analyses.

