The Site Principal Investigator (PI) must apply his/her clinical judgment to determine whether or not an adverse event is of sufficient severity to require that the participant be removed from treatment. The Site PI may consult with the Study EC and the Safety Monitor as needed. If necessary, an Investigator may suspend any trial treatments and institute the necessary medical therapy to protect a participant from any immediate danger. Subsequent review by the Medical Monitor, DSMB, ethics review committee or IRB, the sponsor, or the FDA or relevant local regulatory authorities may also suspend further trial treatment at a site. The study sponsor and DSMB retain the authority to suspend additional enrollment and treatments for the entire study as applicable. A participant may also voluntarily withdraw from treatment due to what he/she perceives as an intolerable adverse event or for any other reason. If voluntary withdrawal is requested, the participant should be asked to continue (at least limited) scheduled evaluations, complete an end-of-study evaluation and be given appropriate care under medical supervision until the symptoms of any adverse event resolve or their condition becomes stable.

A NIDA-assigned Safety Monitor is responsible for reviewing all serious adverse event reports. The monitor will also report events to the sponsor and the Data and Safety Monitoring Board (DSMB). The DSMB will receive summary reports of all adverse events annually, at a minimum.

Serious adverse events will be followed until resolved or considered stable, with reporting to the NIDA assigned Safety Monitor through the follow-up period. The site must actively seek information about the SAE as appropriate until the SAE is resolved or stabilized or until the participant is lost to follow-up and terminated from the study. The Study EC Chair, or the NIDA- assigned Safety Monitor may also request additional and updated information. Details regarding remarkable adverse events, their treatment and resolution, should be summarized by the Investigator in writing upon request for review by the NIDA-assigned Safety Monitor, local ethics Committee/IRBs or regulatory authorities.

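### Section 5.1.5.2 lets a clinic discharge end outcome follow-up, which is not reconciled with the intent-to-treat follow-up rule in 5.1.5.3

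*Protocol*

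**What the plan says.** Protocol section 5.1.5.2 (Study Termination Criteria) provides: "Participants may be involuntarily terminated from all study activities if the site staff" consider that continuing would harm the participant, or "for reasons consistent with CTP discharge policies on violence, drug sale, etc". The two grounds are alternatives. Consulting the Lead Investigator is optional, and the list of clinic-policy reasons is open-ended. The same section then states: "Once randomized, the clinical deterioration, substance use, and the potential need for more intensive care will be captured in assessments".

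Section 5.1.5.3 (Replacement of Participants) sets the general rule: "In this intent-to-treat design, all randomized participants will be followed for all possible assessment points".

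Two neighbouring rules concern leaving treatment, not leaving the study. Section 5.1.5.1 (Therapy Discontinuation) says: "Individuals who are discontinued from the treatment will be encouraged to complete all follow-up assessments". Section 7.14, on voluntary withdrawal from treatment, says: "If voluntary withdrawal is requested, the participant should be asked to continue (at least limited) scheduled evaluations".

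The primary outcome (section 10.3.1) is percent of days of stimulant use, taken from the Substance Use Calendar alone at baseline, weeks 4 and 8, and months 3 and 6. Section 10.5 states that the likelihood estimates are guaranteed unbiased only if data are missing completely at random.

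**The concern.** A clinic discharge ends a treatment relationship. It does not in itself make a research interview impossible, and it is not a withdrawal of consent. Yet 5.1.5.2 lets it end research follow-up as well. Read literally, someone discharged under clinic policy can lose assessments that the protocol still seeks from people who stop treatment for other reasons. About 10 clinics, each with its own discharge policy, may apply the rule differently.

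Two features make this more than a matter of wording. First, the named reasons, violence and drug sale, may be related to the primary outcome. Second, the decision lies with site staff who can know the arm: clinic counselors deliver both conditions (sections 5.1.3 and 6.4), and some research forms in Table 1 are completed for STAGE-12 participants only. If terminations differed by arm, the comparison could be distorted. Because this is a rule about data collection, a later analysis plan could not restore values that were never sought.

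**Working it through.** **The provisions side by side**

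| Event | Section | What happens to outcome follow-up |
|---|---|---|
| Taken off study therapy | 5.1.5.1 | Encouraged in full |
| Voluntary withdrawal from treatment | 7.14 | Requested, at least in part |
| Any randomized participant | 5.1.5.3 | Continues at all possible points |
| Discharge under clinic policy | 5.1.5.2 | May end entirely |

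The first two rows concern treatment and are consistent with 5.1.5.2. The tension lies between the last two rows. The promise within 5.1.5.2 to capture substance use in assessments also cannot be kept once all study activity has stopped. No section exempts research follow-up from a clinic discharge.

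**How large could the effect be?** The protocol states no figure for this, so there is nothing to reproduce. What follows is an illustration on assumed values.

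- From the protocol: target difference 10 percentage points, SD 23.7 points and attrition 30% (section 10.6), with about 200 per arm.
- Assumed: shares terminated, pS (STAGE-12) and pT (TAU), and excess use D, in percentage points, of those terminated over those retained, taken as equal in both arms.

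Within an arm, the full mean equals the retained mean plus p × D, so the observed mean is too low by p × D. The bias in the difference (STAGE-12 minus TAU) is therefore −(pS − pT) × D. In absolute value:

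| Shares terminated | Counts of 200 | D = 10 | D = 25 | D = 50 |
|---|---|---|---|---|
| 2% vs 2%, or 5% vs 5% | 4 vs 4, or 10 vs 10 | 0 | 0 | 0 |
| 2% vs 5% | 4 vs 10 | 0.03 × 10 = 0.3 | 0.03 × 25 = 0.75 | 0.03 × 50 = 1.5 |
| 5% vs 10% | 10 vs 20 | 0.05 × 10 = 0.5 | 0.05 × 25 = 1.25 | 0.05 × 50 = 2.5 |

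Where the shares differ, the range is 0.3 to 2.5 points, or 3% to 25% of the 10-point target. The sign depends on which arm loses more. D = 10 is 10/23.7 = 0.42 SD, while D = 50 is 50/23.7 = 2.1 SD, so the right-hand column is an extreme case. For comparison, 30% attrition is 0.30 × 200 = 60 per arm.

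These figures have two limits. The formula treats those terminated as contributing no data, although their assessments before termination stay in the model. It also describes a difference in means, whereas the primary test in section 10.3.1 concerns the treatment effect on the slope. The figures show an order of magnitude only and do not estimate the bias in the primary parameter.

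**The case against.** The strongest reply is that nothing here is contradictory. Sections 5.1.5.1 and 5.1.5.2 deal with different events, as their headings say. Section 5.1.5.3 promises only the assessments that are possible, and 5.1.5.2 is permissive. On this view there is a general rule with a narrow exception. The reply stands in part: 5.1.5.1 does not conflict, and the qualifier softens 5.1.5.3. But the qualifier most naturally covers people who cannot be reached or who refuse, and the text does not say whether it also covers clinic discharge.

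A reader might infer that the rule removes the primary outcome of heavy users. The documents do not support that. Section 5.1.5.2 names violence and drug sale, not drug use, so heavier use among those removed is an inference. Only data after termination are lost: the model in 10.3.1 allows a varying number of assessments per person.

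A reader might also infer that the missing values are certainly not missing at random and so beyond a likelihood analysis. That is not shown either. If earlier recorded use explains later use, a likelihood analysis can account for it, and section 10.5 also names pattern mixture models. What stands is narrower: discharge for such reasons is unlikely to be missing completely at random, the condition that section 10.5 itself sets.

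Finally, clinic policies are not defined by arm, and nothing suggests that they would be applied unequally. That is true, but the plan also has no safeguard against unequal use.

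**Conclusion.** The point holds as an unreconciled exception to the intent-to-treat follow-up rule, not as a flat contradiction. Followed as written, 5.1.5.2 can give up primary-outcome data that could have been obtained, for reasons that may be related to stimulant use and on the decision of staff who can know the arm. The effect on the result is unknown. It rests on termination rates and excess use that the protocol does not give. It is zero in the arm difference if both are equal across arms, although each arm's mean use would then still be understated if those removed use more. It may be small beside the planned 30% attrition. The 0.3 to 2.5 point range should not be read as a predicted bias. The change is worth making because the loss is avoidable, no analysis can undo it, and the remedy is cheap.

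**What to change.** Reconcile the two sections with a short statement in 5.1.5.2 that discharge under clinic policy does not by itself end outcome follow-up. Substance Use Calendar data would still be sought, by telephone where on-site contact is not permitted, unless consent is withdrawn or the existing ground of harm to the participant applies. Report terminations and their reasons by arm. Table 1 already has a study termination form, and 5.1.5.2 already requires reasons for refusal or withdrawal to be documented, so this adds little collection work. Rules on removal from treatment are unchanged.

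The cost is a small number of telephone contacts, for which the locator information collected at baseline (section 5.4.1.1) can be used. These contacts lose the urine screen that section 5.4.3.1.1 places before the calendar to support the validity of self-report. Calendar data obtained this way should be flagged in the database so that their influence can be examined.

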5.1.5.3 Replacement of Participants

In this intent-to-treat design, all randomized participants will be followed for all possible assessment points. Participants who are randomized to the STAGE-12 intervention but do not attend the initial individual session will not be replaced. Consistent with the intent-to-treat design, attempts will be made to follow these non-attenders in the follow-up assessments and they will be included in the intent-to-treat analyses.

5.2 Number of Sites and Participants

A target of approximately 400 participants from approximately 10 CTPs will be recruited. The goal is to have a sufficient number of interested and qualified CTPs available so that replacement of a CTP can be made in the event of program closure or withdrawal. Each CTP will have approximately 40-50 participants with 20-25 participants in each condition. The overall sample size and number of subjects per participating CTP may be adjusted based on the outcome of a blinded variance check to be conducted after approximately 200 subjects have been randomized (see Section 10.7). An attempt will be made to recruit approximately 50% female participants. In addition, efforts will be made to recruit a sample of study participants that reflects the proportion of minorities in the community where the site is located. Potential participants must satisfy study inclusion and exclusion criteria, listed in section 5.3.3.1

5.3 CTP, Counselor, and Participant Selection

5.3.1 CTP Selection

5.3.1.1 CTP Characteristics

CTPs participating in this protocol should:

- Provide psychosocial (non-opiate replacement) outpatient ambulatory care of sufficient treatment intensity to allow for STAGE-12 group and individual sessions to replace 3 individual and 5 group sessions of TAU each week, for at least 5 weeks during the 8-week intervention phase.
- Have adequate numbers of stimulant-abusing clients seeking outpatient treatment to meet target recruitment goals.
- Have adequate space to accommodate research assistants (RA) and study protocol procedures including on-site urine drug screen (UDS) collection and testing.
- Have a pool of potential counselors from which a minimum of 2 counselors for the STAGE-12 treatment condition can be chosen, willing to:
 - o Participate in this protocol,
 - Be randomly chosen from a pool of eligible counselors to deliver the STAGE-12 intervention,
 - Attend a face-to-face training for STAGE-12 and provide recordings of their sessions to be rated for competence and adherence to the intervention,

 Have at least one clinical supervisor chosen to willingly participate in the protocol, face-toface training, complete an additional training of trainers and have supervision reviewed by a protocol supervisor.

5.3.1.2 Rationale for CTP Selection

The current study is focused on an outpatient intervention and therefore CTPs must provide that level of care to participate in the study. The STAGE-12 intervention is designed to be integrated into the existing outpatient treatment and therefore the CTPs must provide outpatient treatment that meets at least two times per week to allow for the two conditions (TAU and STAGE-12) to be balanced on the amount of treatment available to participants each week. The site selection process will assess the CTPs' treatment frequency, as well as treatment models and client census.

An additional criterion for CTP involvement is based on both the duration of the outpatient program and the minimum number of treatment sessions per week. The STAGE-12 treatment is designed for delivery in a period from 5 up to 8 weeks duration. The CTP must have outpatient programs designed for treatment duration from 5 up to 8 weeks to allow for the two groups to be matched on length of treatment available and to allow for the integration of the study intervention into existing outpatient treatment groups. This time frame for delivery of the STAGE-12 intervention is supported by data on the number of sessions attended by clients in outpatient treatment trials.

The current study will utilize a rolling, or open, admission group process. This will require CTPs to have a sufficient number of new admissions with primary or secondary stimulant use disorders each week to keep both study conditions populated. In addition, participants will need to meet certain study inclusion/exclusion criteria to be enrolled in the study. These inclusion/exclusion criteria represent an additional burden on recruitment and therefore it is expected that only outpatient programs with a high static capacity and a high volume of admissions will be able to meet the study recruitment criteria. Interested CTPs will be evaluated on available participants, staff and facilities to be considered for inclusion as a site in the current study.

Counselors and supervisors will be voluntary participants in the current study. Counselors and supervisors will be required to provide informed consent to be eligible for the study. Each site will require a minimum of two counselors and one supervisor to provide the STAGE-12 intervention and a sufficient number of non-study counselors to maintain the existing TAU services. In addition, CTPs must ensure that the staff participation is fully voluntary; therefore counselors' willingness to participate and their performance in the study will not affect their employment status in any way.

A clinical supervisor will be needed to ensure that counselors are implementing the intervention with an adequate degree of fidelity. The clinical supervisor will fill in for the counselor in the event that the counselor is unavailable. During these periods when the clinical supervisor is seeing participants, he/she will receive supervision from the Lead Node trainer.

The counselor and supervisor trainings require that they attend face-to-face trainings. CTPs will be required to ensure that staff participating in the study will be provided with support to dedicate the necessary effort to complete these trainings and the required training cases in the period of time allowed by the protocol implementation schedule.

